5.4 Selection of Subjects

Selection of Subjects: Patients with a malignant glioma who plan to undergo standard RT with concomitant daily temozolomide (TMZ) therapy

Inclusion Criteria:

- Patients must have histologically-confirmed, newly-diagnosed malignant glioma (glioblastoma, gliosarcoma, anaplastic astrocytoma, anaplastic oligoastrocytoma, anaplastic pleomorphic xanthoastrocytoma, or anaplastic oligodendroglioma) and are scheduled to receive radiotherapy (for a total of 54-60 Gy) and concomitant daily temozolomide therapy (at a dose of 75 mg/m² for one complete 6-week cycle).
- 2. Age ≥ 18 years
- 3. Karnofsky ≥ 60% or ECOG 0-2
- 4. For patients on higher than physiological level of corticosteroids, they must have been on a stable dose for 1 week prior to initiating study drug, and the dose should not be escalated over entry dose level, if clinically possible
- 5. Ability and willingness to give informed consent
- 6. Female patients of childbearing potential must have a negative pregnancy test at Screening
- 7. Female patients of childbearing potential must agree to use an acceptable method of birth control (please refer to the attached document, Birth Control Recommendations (Appendix 18.5)) from the signing of

- informed consent form and to continue its use during the study and for at least 90 days after the final dose
- Male patients must agree to use an acceptable form of birth control (please refer to the attached document, Birth Control Recommendations (Appendix 18.5) from study Day 1 through at least 90 days after the final dose
- 9. Hematocrit >29%, ANC >1,000 cells/mm³, platelets >100,000 cells/ mm³
- 10. Serum creatinine <1.4 mg/dl, bilirubin <1.5 times upper limit of normal
- 11. Aspartate aminotransferase (AST) \leq 2.5 x upper limit of normal range (ULN). For subjects with known liver metastases \leq 5 x ULN, and alanine aminotransferase (ALT) \leq 2.5 x ULN. For subjects with known liver metastases \leq 5 x ULN

Exclusion Criteria:

- Co-medications that may interact with rolapitant as reviewed by Duke Preston Robert Tisch Brain Tumor investigator pharmacist
- Co-medications that are contraindicated in patients on rolapitant including pimozide, thioridazine, carbamazepine, colchicine, dabigatran (Pradaxa), edoxaban (Savaysa), fosphenytoin, metoprolol, phenobarbital, phenytoin, primidone, and warfarin
- 3. Inability or unwillingness to cooperate with the study procedures

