Pharmacodynamics: NK_1 Receptor Occupancy - A Human Positron Emission Tomography (PET) study with rolapitant demonstrated that rolapitant crosses the blood brain barrier and occupies brain NK_1 receptors. A dose-dependent increase in mean NK_1 receptor occupancy was observed in the dose range from 4.5 mg to 180 mg of rolapitant. At the 180 mg dose of rolapitant, the mean NK_1 receptor occupancy was 73% in the striatum at 120 hours after a single dose administration in healthy subjects. The relationship between NK_1 receptor occupancy and the clinical efficacy of rolapitant has not been established.

Cardiac Electrophysiology - In a thorough QT study, rolapitant at doses up to 4 times higher than the recommended dose had no significant effects on the QT intervals

Pharmacokinetics: Absorption - Following a single dose administration of 180 mg rolapitant under fasting conditions to healthy subjects, rolapitant was measurable in plasma between 30 minutes and the peak plasma concentration (C_{max}) for rolapitant was reached in about 4 hours, and mean C_{max} was 968ng/mL (%CV:28%). Following multiple oral doses 9 to 45 mg once daily of rolapitant; accumulation of rolapitant was approximately 5-fold. The systemic exposures (C_{max} and AUC) to rolapitant increased in a dose-proportional manner when the dose of rolapitant increased from 4.5 mg to 180 mg. With an increase in dose by 4 times from the recommended clinical dose of 180 mg, the C_{max} and AUC of rolapitant increased by 3.1 fold and 3.7 fold, respectively. Concomitant administration of a high fat meal did not significantly affect the pharmacokinetics of rolapitant after administration of 180 mg rolapitant.

Distribution - Rolapitant was highly protein bound to human plasma (99.8%). The apparent volume of distribution (Vd/F) was 460 L in healthy subjects, indicating an extensive tissue distribution of rolapitant. In a population pharmacokinetic analysis of rolapitant, the Vd/F was 387 L in cancer patients.

Elimination - Following single oral doses (4.5 to 180 mg) of rolapitant, the mean terminal half-life ($t_{1/2}$) of rolapitant ranged from 169 to 183 hours (approximately 7 days) and was independent of dose. In a population pharmacokinetic analysis, the apparent total clearance (CL/F) of rolapitant was 0.96L/hour in cancer patients.

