Ondansetron: Rolapitant had no significant effects on the pharmacokinetics of intravenous ondansetron when concomitantly administered with a single 180 mg dose of rolapitant on the same day.

CYP2D6 inhibitor:

Rolapitant is a (1) moderate inhibitor of CYP2D6 (i.e. concomitant use with Thioridazine is contraindicated due to QT prolongation and Torsa des de Pointes. Avoid use of rolapitant with pimozide,); (2) an inhibitor of Breast-Cancer-Resistance Protein-BCRP (i.e. Topetecan, Methotrexate; Use the lowest effective dose of rosuvastatin), and (3) an inhibitor of P-glycoprotein (P-gp) (increased plasma concentrations of digoxin, or other P-gp substrates, may result in potential adverse reactions. Monitor for increased digoxin concentrations). Refer to package insert. The Table below is a summary of the effects of the clinical dose of rolapitant on the pharmacokinetics of co- administered drugs:

Table 2: Effects of Rolapitant on the Pharmacokinetics of Co-administered Drugs*

| Enzyme/ transporter | | | % Change for Co-Administered Drug Day 1 with rolapitant Day 8 without rolapitant | | | | |
|------------------------|-----------------------|----------------------------|--|----------------------------|---------------|--|--|
| | | Change in C _{max} | Change in AUC | Change in C _{max} | Change in AUC | | |
| CYP2D6 | Dextromethorphan 30mg | 120% 个 | 160% 个 | 180% 个 | 230% 个 | | |
| BCRP | Sulfasalazine 500 mg | 140% 个 | 130% 个 | 17% 个 | 32% 个 | | |
| P-gp | Digoxin 0.5 mg | 70% 个 | 30% 个 | n/a | n/a | | |

^{*} A single dose of 180 mg rolapitant was administered on day 1; the interacting drug was administered on day 1 with rolapitant and alone on day 8; ↑ Denotes an average increase in exposure by the percentage indicated. n/a: Not studied

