9.4.3 Concomitant Medications

Prophylactic medication for the prevention of nausea and vomiting 24 hours prior to the start of radiation therapy through the full course of radiation therapy is prohibited, with the exception of the study drugs. Corticosteroids will be allowed for treatment of cerebral swelling. Rescue medication for treatment of nausea and vomiting is permitted while receiving radiation therapy at the discretion of the investigator. The date(s) of the rescue medication administration will be recorded in the patient medication log (see appendices).

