12 SCREENING AND ON-STUDY TESTS AND PROCEDURES

Patients will be initially screened during the -28 to 0 days prior to study initiation. During this time period, the following will be recorded: physical examination; vital signs and weight; laboratory studies (complete blood count with differential, platelet, blood chemistries, liver function tests and urinalysis); past medical history; concomitant medications (steroids and anticonvulsants); and predictors of RINV (e.g. irradiation site, planned dose, treatment field, alcohol intake, gender, age). Prior to study enrollment, patient's medications should be reviewed by the clinical pharmacist to prevent concerns with drug interactions. The patient's medications will be evaluated by the PI, the patient's study physician, and/or the study pharmacist on a case by case basis for safety. Laboratory evaluations, performance status, concomitant medications, and adverse events for final eligibility should be confirmed within 2 weeks of initiating radiation with concomitant TMZ.

Patients will be filling out data collection tools (i.e. MAT and TSMQ-9) day 0 (baseline) and days 1, 2, 4, and 7 (for days 7, 1, 2-3, and 4-6, respectively) of each week of radiation therapy. In addition, they will be recording their medication and the use of rescue medication in a medication log as noted below (See Section 12.7 and appendices for study tools).

The CRC will be collecting data from the tools listed below and placing data in an electronic database that is 21CFR Part 11 compliant (e.g. Medidata Rave). Monthly meetings between the CRC and primary investigators will occur to review data. Patient Surveys and follow up phone calls will be conducted weekly to obtain and validate data. The CRC is required to monitor protocol patients weekly or as many times as necessary to obtain toxicities. Toxicities are obtained via clinical notes or telephone conversations with the local oncology office and/or patient. The National Cancer Institute (NCI) Common Toxicity Criteria (CTC) Version 4 is to be used to score the adverse advents. All graded toxicities are then entered in the database and reviewed together with the Primary Investigator (PI) and CRC and confirmed by source documents. Attributions are approved by primary investigators.

Table 7: Screening and Study-related Tests and Procedures

| Phase | Screen | Start | Study Period | | | End | |

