|---|----------------|-------|-------------------------|-------|--------------------|-------|--------------------|
| Week of radiation | -4 to 0 | 1 | 2 | 3 | 4 | 5 | 6 |
| Days of radiation | -28 to 0 | 1-7 | 8- 14 | 15-21 | 22-28 | 29-35 | 36-42 |
| General Evaluations | | | | | | | |
| Informed Consent | Х | | | | | | |
| Eligibility Criteria | X ⁵ | | | | | | |
| Past Medical History | | | | | | | |
| (RINV predictors) | Х | | | | | | |
| Physical Exam | Х | | | | | | |
| Height, Weight, BSA | Х | | | | | | |
| Vital Signs | Х | | | | | | |
| Performance Status | X ² | | | | | | |
| Concomitant Medications | X ² | Х | | | | | |
| Adverse Events | X ² | | Continuous ¹ | | | | |
| Laboratory Evaluations | | | | | | | |
| CBC with Platelets | X ² | | | | | | |
| Serum Chemistry tests | X ² | | | | | | |
| Liver Function tests | X ² | | | | | | |
| Serum Pregnancy Test | X ² | | | | | | |
| Urinalysis | X ² | | | | | | |
| Treatment | | | | | | | |
| Sequence A: Rolapitant (Day) | | | | | X(22) | | |
| Sequence B: Rolapitant (Day) | | X(1) | | | | | |
| Sequence A/B: Daily Ondansetron | | X(1- | X (8- | X(15- | X(22-28) | X(29- | X(36- |
| | | 7) | 14) | 21) | | 35) | 42) |
| Concomitant Temozolomide | | Х | Х | Х | Х | Х | Х |
| Surveys/Medication log | | | | | | | |
| Medication Log | | Х | Х | Х | Х | Х | Х |
| MAT Survey (Day 0 (baseline) and Days 1,2,4,7/week) ³ | Х | Х | Х | Х | Х | Х | Х |
| TSQM9 Sequence A for wks1-3; 4-6 | | | | | X(22)4 | | X(43)4 |
| TSQM9 Sequence B for wks1-3; 4-6 | | | | | X(22) ⁴ | | X(43) ⁴ |

^{1.} Adverse events will be monitored until at least 30 days after the dose of Rolapitant (or 2 weeks after the end of radiation)

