12.2 Treatment Period

The treatment period will consist of six weeks of radiation and concomitant temozolomide as previously described above. Sequence A involves administration of ondansetron alone for 3 weeks followed by the use of

^{2.} Laboratory evaluations, performance status, concomitant medications, and adverse events for final eligibility should be confirmed within 2 weeks of initiating radiation with concomitant TMZ.

^{3.} MASCC questionnaire on Day 0 (baseline), and Days 1, 2, 4, and 7 (for days 7, 1, 2-3, 4-6, respectively)

^{4.} TSMQ-9 administered after week 3 (Day 22) and after week 6 of radiation (Day 43)

^{5.} Eligibility criteria should be checked after informed consent (-4 to 0 weeks) and should be confirmed within 2 weeks of initiating radiation and concomitant TMZ.

rolapitant X 1 dose plus daily ondansetron for 3 weeks; whereas, sequence B involves the use of rolapitant X 1 dose plus daily ondansetron for 3 weeks followed by 3 weeks of daily ondansetron alone. For the rolapitant plus ondansetron weeks (1 or 4), patients will self-administer the oral rolapitant pill 1-2 hours before the first radiation fraction on the planned week (see schema). Subjects will be given a prescription for ondansetron 8mg pills to be taken 30 minutes before their TMZ dose. After the start of radiation therapy, the type of additional rescue antiemetic medication, if needed, will be up to the investigator's discretion. Subjects will be informed that they are allowed to take rescue antiemetic medication in either arm. If the subject experiences nausea and vomiting and does take a rescue antiemetic, the subject will be asked to record the use of additional antiemetic in a medication log provided to them. Subjects will complete weekly medication logs and surveys (see appendices) to capture study outcomes. Subjects will be told that the study is voluntary and that they may exit at any time if they wish.

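### No drug-interaction review is tied to the day-22 rolapitant dose in Sequence A; the interaction exclusions are last confirmed about 22 to 36 days earlier

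*Combined protocol and SAP*

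**What the plan says.** **Interaction review.** Section 12 gives the pharmacist's review one time point: "Prior to study enrollment, patient's medications should be reviewed by the clinical pharmacist to prevent concerns with drug interactions". The next sentence there adds a case-by-case safety evaluation of medications by the PI, the study physician and/or the pharmacist, with no time attached.

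**Confirmation of the exclusions.** Table 7, footnote 5: "Eligibility criteria should be checked after informed consent (-4 to 0 weeks) and should be confirmed within 2 weeks of initiating radiation". Exclusion 1 in Section 5.4 covers interacting drugs as judged by the pharmacist. Exclusion 2 is a list: "Co-medications that are contraindicated in patients on rolapitant including pimozide, thioridazine, carbamazepine, colchicine", followed by eight further drugs, among them several anticonvulsants, anticoagulants and metoprolol.

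**Dosing.** Table 7 and Section 5.11 put rolapitant on day 1 in Sequence B and on day 22 in Sequence A. In both sequences the patient self-administers it (Section 9.4.1).

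**Medications during treatment.** Section 9.4.3 carries one prohibition through the course of radiation: "Prophylactic medication for the prevention of nausea and vomiting 24 hours prior to the start of radiation therapy". It also deals with corticosteroids and rescue medication. It does not mention the exclusion 2 list.

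**Pharmacology.** Section 7.2 says the half-life "of rolapitant ranged from 169 to 183 hours (approximately 7 days) and was independent of dose". It also says that "concomitant use with Thioridazine is contraindicated due to QT prolongation and Torsa des de Pointes".

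**The concern.** The safeguard against giving rolapitant with a listed drug is built around study entry. That suits Sequence B, where entry and dosing nearly coincide. In Sequence A three weeks of chemoradiation come between. Local radiation and oncology clinicians follow patients in that time (Sections 9.1 and 9.3), so a new prescription could come from outside the study team. The exclusion 2 list includes carbamazepine, phenytoin, fosphenytoin, phenobarbital and primidone, and Section 5.2 names enzyme-inducing anticonvulsants among drugs commonly used in glioma patients. A new start within three weeks is therefore plausible, although the documents give no rate.

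What is at stake is safety. One long-acting dose cannot be taken back, and the documents link at least one listed drug, thioridazine, to a serious arrhythmia when combined with rolapitant. Because exposure lasts for weeks, a listed drug started soon after dosing matters too, and that applies to both sequences.

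**Working it through.** The plan states no interval, so there is no figure of its own to reproduce. The check is day arithmetic, a decay calculation and a head count.

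**1. Interval from each check to the Sequence A dose.** Formula: 22 minus the day of the check.

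| Check | Source | Day of check | Days before day 22 |
|---|---|---|---|
| Pharmacist interaction review | Section 12; earliest case is the start of screening | -28 at the earliest | 22 - (-28) = 50 at most |
| Confirmation of exclusions 1 and 2 | Table 7, footnote 5 | -14 to 0 | 22 - 0 = 22, up to 22 - (-14) = 36 |
| Concomitant-medication entry | Table 7, week 1 column | 1 to 7 | 22 - 7 = 15, up to 22 - 1 = 21 |

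If the two weeks are counted back from day 1, the second row becomes 21 to 35. The 50 days is an upper bound, since the text says only that the review precedes enrolment. In the third row, the blank cells for weeks 2 to 6 may be an artefact of text extraction. If the week 1 cell was merged across the study period, recording continues up to the dose.

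**2. What the later provisions are described as doing.**
- Week 1 entry in Table 7: recording of medications.
- Medication log, weeks 1 to 6 (Table 7, Section 12): the patient records medication and rescue use.
- Weekly call before week 4 (Section 9.4.2): a reminder to take ondansetron and rolapitant.
- Weekly questioning by the coordinator (Section 10.5): compliance.
- Weekly follow-up calls and monitoring (Section 12): data validation and toxicity.
- Dispensing by the study pharmacist (Section 10.4): no date and no re-check stated.
- Self-report of drugs to the study doctor (Section 5.8): ongoing, untimed.
- Case-by-case evaluation (Section 12): untimed.

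Several of these could bring a new drug to light. None is described as an interaction review that must precede the day-22 dose. The log forms (Appendices 3 and 4) are not in the text available and are not counted against the plan.

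**3. How long a dose remains.** Assume simple exponential decline, with the half-life of 169 to 183 hours from Section 7.2. Fraction remaining = 0.5^(t / half-life).
- 7 days (168 h): 0.5^(168/169) = 0.502; 0.5^(168/183) = 0.529.
- 21 days (504 h): 0.5^(504/169) = 0.127; 0.5^(504/183) = 0.148.

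About half remains after a week and 13 to 15% after three weeks. The enzyme effect does not fade over the first week. In Table 2, where "the interacting drug was administered on day 1 with rolapitant and alone on day 8", dextromethorphan (CYP2D6) AUC rose by 160% on day 1 and by 230% on day 8.

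**4. Reach.** Section 15.4 gives 53 randomised by mid-January 2022 and a target of 57. Left to randomise: 57 - 53 = 4. At 1:1 allocation, 4 x 0.5 = 2 are expected in Sequence A. Any Sequence A patients already randomised but not yet at day 22 add to this; the number is not given.

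**The case against.** The strongest reply is that medications are not ignored after entry. Table 7 has a concomitant-medication entry in week 1, later than the eligibility confirmation, and it may have spanned more weeks in the source layout. Section 15.4.2 plans to use the decadron dose in each treatment segment as a covariate, which requires at least steroid data in the second period. There are weekly logs, calls and coordinator questioning, and one call is linked to the week 4 dose. Patients are told to report all drugs, medications are to be evaluated for safety, and a pharmacist dispenses as the study team directs. The package insert is the reference safety information (Section 5.8), so labelled contraindications already guide prescribers. Harm would need several of these layers to fail.

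Most of this stands. A reader might infer from the 22 to 36 days that nobody looks at medications between the eligibility confirmation and day 22. The documents do not support that: the figure applies only to the last timed confirmation of exclusions 1 and 2, and medication recording continues after it.

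The reply does not supply a review. Recording a drug is a different step from checking it against the list, and the untimed provisions do not require either step before the dose. Self-report is also a weak sole backstop in patients whom Section 7.3 describes as prone to forget medicines because of memory impairment.

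**Conclusion.** The point holds in a limited form. No interaction review is tied to the day-22 dose in Sequence A. The exclusions were last confirmed about 22 to 36 days earlier, and the only interaction review with a stated time precedes enrolment. In Sequence B the same checks sit close to the dose. Section 9.4.3 does not carry the contraindicated-drug list into the treatment period for either sequence.

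This is a safety improvement worth considering, with small reach: about 2 further Sequence A patients expected, plus an unknown number not yet dosed. Without a rate of newly started listed drugs, no event count can be estimated. The interval rests on reading the confirmation window as day -14 to day 0.

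A reader might go further and infer bias in the results. The documents do not support that. The primary endpoint covers weeks 1 and 2, before the Sequence A dose, and nothing in the documents shows an effect on second-period or preference data. Nor do they show that any patient has been dosed while on a listed drug.

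**What to change.** 1. At the weekly call just before day 22 in Sequence A, ask about all current medications. Repeat the existing pharmacist interaction review before the dose is taken, and mark the step in Table 7.
2. State in Section 9.4.3 that the exclusion 2 list applies at rolapitant dosing and for a period afterwards set by the investigators, in both sequences.

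What to do about a positive finding stays with the investigators.

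The cost is one question in a call already planned, a short pharmacist check for each undosed Sequence A patient, a mark in Table 7 and one sentence in Section 9.4.3. The downside is that a patient found on a listed drug may miss rolapitant and so leave the preference analysis, which Section 15.1 limits to patients who have experienced both regimens.

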12.1 Screening Examination

The screening examination will take place between Day -28 and 0. Laboratory evaluations, performance status, concomitant medications, and adverse events will be confirmed within 2 weeks of initiating radiation and concomitant TMZ. An informed consent will be signed by the patient before any screening procedure takes place. Subject data to be collected at the Screening Examination as listed above in **Table 7** includes the following: physical examination; vital signs and weight; laboratory studies (complete blood count with differential, platelet, blood chemistries, liver function tests, urinalysis, and Beta-HG); past medical history; concomitant medications (steroids and anticonvulsants); and predictors of RINV (e.g. irradiation site, planned dose, treatment field, alcohol intake, gender, age).

If a subject is found to be ineligible to participate in the study, minimal records regarding the subject and the reason for screen failure will be retained in the study database.

12.2 Treatment Period

The treatment period will consist of six weeks of radiation and concomitant temozolomide as previously described above. Sequence A involves administration of ondansetron alone for 3 weeks followed by the use of

^{2.} Laboratory evaluations, performance status, concomitant medications, and adverse events for final eligibility should be confirmed within 2 weeks of initiating radiation with concomitant TMZ.

^{3.} MASCC questionnaire on Day 0 (baseline), and Days 1, 2, 4, and 7 (for days 7, 1, 2-3, 4-6, respectively)

^{4.} TSMQ-9 administered after week 3 (Day 22) and after week 6 of radiation (Day 43)

^{5.} Eligibility criteria should be checked after informed consent (-4 to 0 weeks) and should be confirmed within 2 weeks of initiating radiation and concomitant TMZ.

rolapitant X 1 dose plus daily ondansetron for 3 weeks; whereas, sequence B involves the use of rolapitant X 1 dose plus daily ondansetron for 3 weeks followed by 3 weeks of daily ondansetron alone. For the rolapitant plus ondansetron weeks (1 or 4), patients will self-administer the oral rolapitant pill 1-2 hours before the first radiation fraction on the planned week (see schema). Subjects will be given a prescription for ondansetron 8mg pills to be taken 30 minutes before their TMZ dose. After the start of radiation therapy, the type of additional rescue antiemetic medication, if needed, will be up to the investigator's discretion. Subjects will be informed that they are allowed to take rescue antiemetic medication in either arm. If the subject experiences nausea and vomiting and does take a rescue antiemetic, the subject will be asked to record the use of additional antiemetic in a medication log provided to them. Subjects will complete weekly medication logs and surveys (see appendices) to capture study outcomes. Subjects will be told that the study is voluntary and that they may exit at any time if they wish.

